Evaluation of the Safer Bars Prevention Program for Sexual Assault

NCT: 04141839

Date: March 13, 2025

Study Protocol and Statistical Analysis Plan

Study Protocol

The objectives of the protocol are to conduct a cluster-randomized controlled trial with crossover, multiple sources of data, and a theory-driven analysis plan to assess the immediate and intermediate effectiveness of *Safer Bars*, a primary perpetration prevention program to train bar staff to recognize and respond to sexual aggression and its precursors among patrons. This prospective evaluation will assess individual-level outcomes, including changes in bar staff members' attitudes, perceived social norms, perceived behavioral control, behavioral intent, and subsequent bystander behavior. Bar-level outcomes will include changes in the physical bar environment and risk management safety policies. Additionally, we will use GIS mapping to identify "hot spots" of liquor licenses in areas within a 3-mile radius of the three major Arizona universities and map police dispatches for reports of sexually-violent behavior in these areas prior and subsequent to the intervention in order to assess community-level outcomes.

Recruitment. The study will recruit approximately 56 bars with an average of ten participants per bar for an intended sample size of 564 individual bar staff and 56 bar owners/managers. Sampling of bars will be proportional to the size of student enrollment at each of the universities. The study will sample from bars that are located within 3 miles of the university campuses, have a current liquor license to serve on-premises, and have not received the *Safer Bars* training within the past year.

Project staff will generate a list of bars in the catchment areas and will contact their owner/managers through combinations of email, phone, social media, and in-person visits. If a bar owner/manager is interested in receiving more information, staff will describe the training and study, as well as provide informational material. If a bar agrees to participate, the owner/manager will sign the Bar Agreement Form, which details the time commitment and study details. Project staff will then utilize a block randomization procedure to determine which arm (control or intervention) the bar is in and will convey this to the owner/manager as well as details about the monetary incentive (\$250) available to cover some of the costs of hosting the study at their establishment. Research staff may also recruit through organizations or associations related to bartending, bartenders, or bar owner/managers within the specified catchment areas. Bars may receive *Safer Bars* training without participating in the study.

Before training session 1 (intervention group) or the information session (control group), research staff will meet with the bar owner/manager to review the consent form and screening questions. If the bar owner/manager is eligible and agrees to participate, they will provide informed consent and their contact information. At the beginning of training session 1 (intervention group) or the information session (control group), staff will discuss the study with the bar staff, provide them the opportunity to ask questions, assess eligibility, and obtain informed consent and contact information. Individuals who do not wish to participate in the study may still attend the training.

Retention. We will take multiple steps to retain participants throughout the project. First, we will make participation as convenient as possible by using in-person data collection for the baseline surveys and online data collection for the follow-up surveys. Second, we will give reminders to participants regarding survey completion. Finally, we will structure our payment and incentive schedule to encourage full completion.

Study Design. A 6-month, cluster-randomized controlled trial study design will be implemented. Bars (n = 56 bars; n = 564 bar staff; n = 56 bar owners/managers) will be randomized to receive either the *Safer Bars* bystander promotion intervention or will be assigned to a waitlist control condition in which they receive the *Safer Bars* intervention after a 3-month waiting period. Participants working at bars in the intervention group will receive two, 2.5-hour in-person intervention sessions spaced approximately two weeks apart coupled with assessments preintervention session 1 (baseline) and immediately post-intervention session 2. They will then complete follow-up assessments at 3 months and 6 months post-intervention. Participants working at bars assigned to the waitlist control group will complete an initial information session about the study in which they respond to the same baseline measures as the intervention group, followed by a 3-month assessment identical to that of the intervention group. Control bars will then be eligible to receive the *Safer Bars* intervention.

Statistical Analysis Plan

Individual-level Analyses

Because randomization to study arm will be at the bar level, we will use analytic techniques (generalized linear mixed models [GLMMs] and multilevel structural equation models [MSEMs]) that account for clustering of individuals nested within bars and repeated measures within individuals and allow for participant-level missing data [18,19,20]. Selection of model link functions (e.g., identity, log, logit) and error distributions (e.g., normal, Poisson, binomial) in GLMMs and MSEMs will be guided by the scale of measurement and observed distribution of the outcome measure. To test program effects on bystander behavior, we will estimate GLMMs predicting bystander behaviors at follow-up, adjusting for baseline bystander behavior as well as any relevant covariates identified in preliminary analyses. GLMMs will include random components for bar-level intercepts. To address mediation of program effects via TPB constructs, we will estimate prospective MSEMs in which the effect of study arm on bystander behavior is mediated through its effects on TPB constructs. Point estimates of indirect effects will be computed using a product-of-coefficients approach [21]. As MPlus does not produce bootstrap standard errors for indirect effects in multilevel SEMs, Bayesian credible intervals will used for inference. To address potential moderation of program effects by participant characteristics (gender identity, job position, education, personal sexual assault experiences, prior education in sexual assault prevention) and bar characteristics (policies, physical environment), we will extend above GLMMs by including Study Arm x Characteristic interaction terms. Each significant interaction will be probed to characterize the pattern of differential program effects across categories or levels of a background characteristic [22].

Bar-level Analyses

Within a generalized linear modeling framework, a series of ANCOVAs will be conducted to examine the effect of intervention condition on changes in physical environment characteristics and risk management safety policies. Outcome scores at 3-month follow-up will be predicted from study arm, adjusting for baseline scores and relevant bar-level covariates. The Sidak procedure will be used to control study-wise Type 1 error inflation.

Community-level Analyses

Violent crime datasets will be obtained from relevant municipal police departments via public records requests for years prior to and during the study. Maps will be generated using ArcGIS ArcMap. Violent crimes of interest will be mapped using the "Esri World Geocoder" under the "Geocode Addresses" tool and then shapefile layers will be created.

Next, spatial information of the liquor licenses for the relevant bars will be obtained from the Arizona Department of Liquor Licenses and Control (DLLC) website. Only "on-premises" liquor license addresses will be queried and mapped. Shapefile layers of bar locations will be created and added to the maps. Utilizing the "Kernel Density" tool within the "Spatial Analyst

Toolbox" via ArcMaps, bar location density will be mapped against the crime points. The results will illustrate the amount of violent crime in a specific location in relation to the density of bars for that exact location. Analyses will compare the frequency of violent crime-related police dispatches to study catchment areas before and after receiving *Safer Bars* training.

Power Analysis

The sample size of 564 individual bar staff (approximately 56 bars [28 bars in each study arm] x average of 10 participants per bar) affords power of .80 to detect small-to-moderate standardized between-group differences (i.e., intervention effects) on individual-level outcomes ranging from d = 0.28 to 0.45, depending on an assumed intraclass correlation (ICC) of .10 for outcome scores, assumed correlations between baseline and follow-up scores ranging from r = .10 to .50, and assumed ICCs for pre-post change scores ranging from .05 to .10. Adjusting for bar-level clustering, the proposed sample should afford power of .80 to detect indirect effects and small-to-moderate constituent direct effects (ds= 0.35-0.45 for X to M, r2s = .04-.09 for M to Y), assuming a 10% attrition rate. For bar-level outcomes, the proposed sample size affords power to detect large effects (ds = 0.66-0.76, for pre-post correlations of r = .10-.50).

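### Bar staff are screened, consented and surveyed at baseline only after their bar is allocated, at sessions that differ by arm, so who enrols within bars can differ by arm

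*Combined protocol and SAP*

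**What the plan says.** Recruitment (Study Protocol) sets the order of events. The owner/manager signs the Bar Agreement Form, and project staff then "utilize a block randomization procedure to determine which arm (control or intervention) the bar is in and will convey this to the owner/manager". The owner/manager is screened and consented after that.

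The staff step comes later still: "At the beginning of training session 1 (intervention group) or the information session (control group), staff will discuss the study with the bar staff". In the same step the research team will "provide them the opportunity to ask questions, assess eligibility, and obtain informed consent and contact information". People who decline the study may still take the training.

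Study Design places the intervention-arm baseline before session 1, the first of two 2.5-hour sessions. Control-arm staff "complete an initial information session about the study in which they respond to the same baseline measures as the intervention group", and their bars become eligible for the training after the 3-month assessment.

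Individual-level Analyses says the models will "account for clustering of individuals nested within bars and repeated measures within individuals and allow for participant-level missing data". Bystander behavior at follow-up is modelled with bar-level random intercepts, "adjusting for baseline bystander behavior as well as any relevant covariates identified in preliminary analyses". Power Analysis uses "assumed correlations between baseline and follow-up scores ranging from r = .10 to .50".

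The documents describe no staff list fixed before allocation, no common opening script, no delayed announcement of the arm to staff, and no count of eligible against enrolled staff.

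**The concern.** Bars commit before allocation, so randomization protects which bars are in the trial. It does not protect which people within a bar are in the trial. When staff decide whether to attend and enrol, the owner/manager already knows the arm, and the occasion itself (a training or an information session) can reveal it. The two occasions also ask different things of staff.

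The individual-level comparison is between those who enrolled. If enrolment differs by arm and is linked to later bystander behavior beyond what the baseline score captures, part of the estimated program effect is selection. The planned analysis does not cover this. Bar random intercepts deal with correlation within bars, the missing-data provision concerns enrolled participants, and the further covariates are left to preliminary analyses.

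**Working it through.** **1. The plan's own figure.** From Power Analysis: 564 staff, 28 bars per arm, about 10 staff per bar, ICC .10 for outcome scores and .05-.10 for change scores, r = .10-.50, power .80. Two-sided 5% alpha is my assumption, since none is stated. Detectable d = (1.960 + 0.842) x SE.

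- Change scores, SE = sqrt[(4/564)(1 + 9 x ICC) x 2(1 - r)]: r = .50 and ICC .05 give SE 0.1014, d = 0.284; r = .10 and ICC .10 give SE 0.1557, d = 0.436 (0.445 with a t reference based on the number of bars). This matches the stated 0.28-0.45 closely.
- Baseline-adjusted (ANCOVA) scores, with (1 - r^2) in place of 2(1 - r), at ICC .10: SE 0.1005 (d = 0.282) at r = .50, and SE 0.1155 (d = 0.324) at r = .10.

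The power figure does not depend on when staff enrol. Below I use the ANCOVA SEs at ICC .10, because the planned model adjusts for baseline and .10 is the ICC given for outcome scores.

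**2. What baseline adjustment removes.**

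- Selection shifts baseline and follow-up equally, by s: the residual is s - r x s = (1 - r)s, which is 0.50s at r = .50 and 0.90s at r = .10.
- Joining depends only on measured baseline behavior: follow-up shifts by r x s, so the residual is r x s - r x s = 0.

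**3. Size on assumed values.** The documents give neither participation rates nor the correlation rho between joining and behavior. With a proportion p joining, the mean shift among joiners is rho x phi(z_p)/p. The multiplier phi(z_p)/p is 0.195 at 90%, 0.350 at 80%, 0.497 at 70% and 0.644 at 60%. I take the same rho in both arms, equal shifts at both times, a true effect of zero and no attrition. The top rho is .5 at r = .50. At r = .10 it is capped at sqrt(.10) = .316, where joining alone would account for the whole baseline to follow-up correlation. The false-positive rate is P(|Z + residual/SE| > 1.96).

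Example, 90% vs 70%, rho = .5, r = .50: raw shift 0.5 x (0.497 - 0.195) = 0.151; residual 0.50 x 0.151 = 0.075; 0.075/0.1005 = 0.75; false-positive rate 11.7%.

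| Participation gap | r | rho | Residual bias (SD) | False-positive rate |
|---|---|---|---|---|
| 10 points (90 vs 80%, 80 vs 70%) | .50 | .1 | 0.007-0.008 | 5.1% |
| | .10 | .1 | 0.013-0.014 | 5.2% |
| | .50 | .5 | 0.037-0.039 | 6.5-6.7% |
| | .10 | .316 | 0.042-0.044 | 6.5-6.7% |
| 20 points (90 vs 70%, 80 vs 60%) | .50 | .1 | 0.015 | 5.2-5.3% |
| | .10 | .1 | 0.026-0.027 | 5.6% |
| | .50 | .5 | 0.073-0.075 | 11.3-11.7% |
| | .10 | .316 | 0.084-0.086 | 11.2-11.5% |

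Simulation (1.5 million per arm before joining) shows the formula is slightly low at the top: for 90 vs 70%, r = .50, rho = .5 it gives 0.082-0.084 rather than 0.075, which is a false-positive rate of about 13%. Selection narrows the baseline scores and so lowers the adjustment slope.

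**4. Equal participation is not enough.** Suppose 80% join in both arms, with rho = .3 in one and .1 in the other. The raw shift is (0.3 - 0.1) x 0.350 = 0.070, and the residual is 0.035 at r = .50 and 0.063 at r = .10 (0.036 and 0.064 by simulation).

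**The case against.** The plan already has real protections. Bars agree before allocation, staff consent is placed at the start of the session, the intervention-arm baseline precedes the training, and both arms use the same baseline measures. Control bars are promised the training, and nobody has to join the study to be trained, so the pull to enrol in one arm is weaker than in many trials. The analysis adjusts for baseline behavior and possibly more, and the illustration ignores those extra covariates. If the link function is not the identity, the (1 - r) rule need not carry over exactly. At rho = .1 the bias is negligible, and the top rows of the table sit at a boundary that nothing in the documents supports. All of this stands; it narrows the risk and limits how far the figures can be pressed, but it does not remove the risk.

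Two stronger readings are tempting. A reader might infer that staff are told their arm before they consent. No section says so; the text supports only that the owner/manager knows and that the type of session can reveal it. A reader might also infer that a common script or a two-condition consent text has been ruled out. The text is short and the consent pages are not in the file, so the most that can be said is that none is described.

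**Conclusion.** The point holds as a design risk worth a cheap correction. Staff enter after allocation at arm-specific sessions, and nothing in the planned analysis corrects for who enrols, except where joining depends only on measured baseline behavior.

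The size rests on assumed participation rates, rho and alpha. It runs from negligible (about 0.01 SD) to about 0.09 SD. Set against the matching ends of the plan's range, the largest formula values are 0.075/0.28 = 27% at r = .50 and 0.086/0.45 = 19% at r = .10. These are illustrations, not estimates.

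A reader might infer that the enrolled groups did differ, or that the bias favors the intervention. The documents support neither: they report no enrolment, and selection could run in either direction. Nor would similar participation rates prove that there is no bias, because the link between joining and behavior may itself differ by arm. Confidence is medium.

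**What to change.** - **(a) Main change.** In both arms, complete staff eligibility, consent and the baseline survey under one common opening script and a consent text that covers both conditions, before the arm or the session content is announced to staff.
- **(b) Supporting change.** Record the number of eligible staff per bar, without names, when the Bar Agreement Form is signed and before the allocation is drawn. Report eligible, approached and enrolled staff, and baseline characteristics, by arm.
- **(c) If enrolment is already finished** (the documents do not say), report these figures where counts exist and add a sensitivity analysis for differential enrolment.

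The cost is small: (a) standardizes steps that already take place at the session, (b) adds one count per bar at a signing that already happens, and the burden is slight scheduling effort. Neither is a full cure. Under (a) the owner/manager still knows the arm and attendance still precedes consent, so the bias is reduced but not removed; (b) describes differential enrolment but does not prevent it.

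### Owner/manager screening and consent follow disclosure of the bar's arm, so owner participation, and any bar-level baseline taken from owners, can depend on allocation

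*Combined protocol and SAP*

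**What the plan says.** The Recruitment text of the Study Protocol sets out an order of events.

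1. Commitment of the bar: "If a bar agrees to participate, the owner/manager will sign the Bar Agreement Form, which details the time commitment and study details".
2. Allocation, and disclosure of the arm to the person who signed: "Project staff will then utilize a block randomization procedure to determine which arm (control or intervention) the bar is in and will convey this".
3. Owner screening and consent, at a meeting described separately for each arm and held before training session 1 or the information session: "research staff will meet with the bar owner/manager to review the consent form and screening questions". Participation is conditional at this step: "If the bar owner/manager is eligible and agrees to participate, they will provide informed consent and their contact information".

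The same text allows bars to have the training without being in the study.

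Under Study Design, the intervention arm has "assessments preintervention session 1 (baseline) and immediately post-intervention session 2", and controls attend an "initial information session about the study in which they respond to the same baseline measures as the intervention group". Both baselines come after the arm has been conveyed, and both are described for people working at the bars.

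The SAP, under Bar-level Analyses, covers physical environment and risk management policies: "Outcome scores at 3-month follow-up will be predicted from study arm, adjusting for baseline scores and relevant bar-level covariates". It does not say who supplies these scores or when the baseline is taken. The provision for missing data, under Individual-level Analyses, is at participant level only.

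**The concern.** Randomization protects a comparison only for units and measurements fixed before allocation is known. Here two things are settled afterwards.

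The first is whether the owner is found eligible and agrees to take part. An owner told to wait three months has a possible reason to decline the study and ask for the training outside it. An owner allocated to immediate training has no such reason. Loss of owner data that differs by arm would undermine a bar-level comparison of only 56 bars.

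The second is any bar-level baseline that comes from the owner. Owners presumably have a large say in the policies being scored. One who expects training soon may tighten policies early, or describe them more favourably or more critically. The ANCOVA would then adjust for a covariate already affected by allocation, and the estimated effect would absorb part of that shift.

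**Working it through.** **Inputs from the documents (Power Analysis).** 28 bars per arm; pre-post correlation r = .10 to .50; detectable bar-level d = 0.66 to 0.76. Power of .80 is stated for individual-level outcomes and taken to apply here too.

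**Assumptions.** Two-sided alpha of 0.05 (not stated); equal baseline and follow-up SD, so that the ANCOVA slope equals r; every shift and loss figure below.

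**1. The plan's own figure.** With SE = sqrt[(1 − r²)(1/28 + 1/28)] and a noncentral t on 28 + 28 − 3 = 53 df, the detectable effect at power .80 is:
- r = .10: d = 0.759
- r = .50: d = 0.660

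This reproduces 0.66–0.76. It uses all 28 bars in each arm, so the bar-level figure makes no allowance for lost bars.

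**2. Precision if bar-level data are lost in one arm.** Same formula, with fewer bars in one arm; power is at d = 0.76 (r = .10) and d = 0.66 (r = .50).

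| Bars | Detectable d, r = .10 | Detectable d, r = .50 | Power at the design effects |
|---|---|---|---|
| 28 vs 28 | 0.759 | 0.660 | 0.801, 0.799 |
| 28 vs 25 | 0.782 | 0.681 | 0.777, 0.775 |
| 28 vs 22 | 0.811 | 0.706 | 0.747, 0.745 |

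The loss of power is modest.

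**3. Bias if the loss is selective.** If k of 28 bars are lost and differ from the retained bars by D SD on the outcome, the arm mean moves by (k/28) × D:
- k = 3: 3/28 × 0.5 = 0.054 SD; 3/28 × 1.0 = 0.107 SD
- k = 6: 6/28 × 0.5 = 0.107 SD; 6/28 × 1.0 = 0.214 SD

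Baseline adjustment would recover part of this only to the extent that baseline predicts the difference.

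**4. Bias if the baseline is shifted by allocation.** If the intervention arm's recorded baseline is shifted by s SD relative to control, the expected ANCOVA effect is (true effect) − r × s.

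| Assumed s | Bias, r = .10 | Bias, r = .50 | Approximate type I error, r = .10 and .50 |
|---|---|---|---|
| 0.2 | 0.1 × 0.2 = 0.02 | 0.5 × 0.2 = 0.10 | 0.051, 0.071 |
| 0.5 | 0.1 × 0.5 = 0.05 | 0.5 × 0.5 = 0.25 | 0.054, 0.185 |

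Simulation agrees with the bias formula. The type I figures use the SE from step 1. They ignore the slightly larger SE that a baseline imbalance brings, so the largest is a little high.

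The sign is opposite to the shift: a better-looking intervention baseline understates benefit, and a worse-looking one overstates it. Against the detectable effect, a 0.2 SD shift costs 0.02/0.759 = 3% at r = .10 and 0.10/0.660 = 15% at r = .50.

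**The case against.** The strongest reply is that the order of events is as described, but little follows from it with certainty.

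- **The bar commits before allocation.** The Bar Agreement Form is signed first and sets out the time commitment. That is real protection, and it stands. It is incomplete, because owner consent and screening remain open afterwards and training is available outside the study.
- **A reader might infer that an owner's refusal removes the whole bar.** The documents do not say so. They count 56 owners/managers separately from 56 bars; the later consent enrols the owner as a participant; and the bar criteria (location, licence, no recent training) apply at sampling. Nothing says that an ineligible or unwilling owner takes the staff out of the analysis. The exposure is clearest for bar-level data that need the owner. The plan also has no rule for this case.
- **A reader might infer that the ANCOVA baseline is contaminated.** The documents do not establish this either. They do not say that owners supply the policy or environment scores, and the protocol refers to multiple data sources. An observer's rating, or one made before disclosure, would weaken the point. No such rating is described, and the only scheduled baselines follow disclosure.
- **The sizes rest on assumed shifts.** This is correct, and at r = .10 the bias is small.

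The stated sequence survives all four replies: owner eligibility and consent are decided with the arm known.

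**Conclusion.** The concern holds in a limited form. It is a weakness in a stated sequence, and the missing source and timing of the bar-level baseline make it harder to judge. Post-allocation selection of owners, and a baseline that depends on the arm, are both possible under the plan as written. Neither is shown to occur.

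If an owner-reported baseline is shifted by an assumed 0.2 SD, the bar-level effect is biased by 0.02 to 0.10 SD over the plan's range of r, in either direction. The problem matters mainly near r = .50 or with larger shifts. Selective loss of bar-level data is the other route, and its size depends wholly on how many bars are affected and how they differ. The stated detectable effects of 0.66–0.76 are correct for 28 bars per arm and would not change with the fix; the gain is removal of a possible bias. The point concerns bar-level outcomes and owner participation, not which staff enrol within a bar. It should be addressed, because the reordering is cheap.

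**What to change.** **Recruitment.** After the Bar Agreement Form is signed, complete owner/manager screening, informed consent and any owner-reported policy baseline, in person or remotely. Only then run the block randomization and convey the arm.

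**Bar-level Analyses.** Define the baseline score as this pre-allocation score and state its source. Analyse every randomized bar in its assigned arm, say how a bar is handled if its owner is ineligible or declines, and report bar and owner losses after randomization by arm.

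**Environment rating.** If an on-site rating cannot be made before randomization, state when it is made and by whom, and add a sensitivity analysis that does not adjust for that baseline.

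**Cost.** The owner contact becomes earlier or longer. It may have to be a separate one, since no signing meeting is described and recruitment contact may be by email, phone or social media. Some baselines will come from owners who then do not proceed. An environment rating before randomization could need an additional visit, hence the fallback.

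### Bar-level multiplicity: naming the step-down Holm-Sidak form instead of the Sidak procedure would be an optional, nearly free gain in efficiency, sized from about 0 to 12 points of power per outcome depending on how many outcomes respond

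*Combined protocol and SAP*

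**What the plan says.** Under Bar-level Analyses, the SAP says that "a series of ANCOVAs will be conducted to examine the effect of intervention condition on changes in physical environment characteristics and risk management safety policies". The model is a baseline-adjusted comparison: "Outcome scores at 3-month follow-up will be predicted from study arm, adjusting for baseline scores and relevant bar-level covariates". The section closes with "The Sidak procedure will be used to control study-wise Type 1 error inflation". It does not say whether the single-step or the step-down form is meant, how many tests there are, or at what alpha level.

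The Power Analysis section assumes "approximately 56 bars [28 bars in each study arm", and for these outcomes it reports: "For bar-level outcomes, the proposed sample size affords power to detect large effects (ds = 0.66-0.76, for pre-post correlations of r = .10-.50". It does not mention the Sidak correction there.

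**The concern.** Single-step Sidak tests each of k outcomes at 1 − (1 − α)^(1/k), however many of the others have already been rejected. Holm-Sidak orders the p-values, tests the smallest at that same threshold, and tests each later one at a looser threshold based on the number of hypotheses still open. Both rest on the same probability inequality.

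The choice matters because only about 56 bars inform these outcomes, and the plan itself expects to detect only large effects. One training programme is meant to shift both the physical environment and the safety policies, so several outcomes responding together is plausible. That is the situation in which the step-down form finds effects that the single-step form misses.

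**Working it through.** **Inputs from the plan:** 28 bars per arm; d = 0.66 at r = .50 and d = 0.76 at r = .10; ANCOVA adjusting for baseline.

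**Assumptions, because the plan is silent:** two-sided α = .05; power .80 (stated only for individual-level outcomes); k from 2 to 10 (two domains are named, so at least 2); correlation between test statistics from 0 to .8; no loss of bars.

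**Step 1. Reproduce the plan's figure.** With noncentrality d / [√(1 − r²) × √(2/28)] and 53 degrees of freedom:
- r = .50: 0.66 / (0.866 × 0.267) = 2.85, power 79.9%
- r = .10: 0.76 / (0.995 × 0.267) = 2.86, power 80.1%

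The stated range therefore corresponds to 80% power for one uncorrected two-sided .05 test. The two settings have nearly the same noncentrality, so d = 0.66 at r = .50 is used below.

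**Step 2. Compare thresholds.** Single-step Sidak uses 1 − .95^(1/k) throughout: .0253 for k = 2 and .0127 for k = 4. At step j, Holm-Sidak uses 1 − .95^(1/(k − j + 1)). For k = 4 these are .0127, .0170, .0253 and .0500. Any p-value at or below .0127, and every p-value smaller than it, passes its step. So Holm-Sidak makes every single-step rejection, whatever k, the effects or the correlation may be. The first step is identical, so the chance of at least one rejection is identical.

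**Step 3. Size of the gain.** Simulation of correlated ANCOVA t statistics, 200,000 replicates per setting. With every outcome at the detectable effect and correlation .3:

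| k | Mean power per outcome, single-step | Holm-Sidak | Power for all k, single-step | Holm-Sidak |
|---|---|---|---|---|
| 2 | .71 | .77 | .54 | .66 |
| 4 | .61 | .71 | .23 | .46 |
| 6 | .55 | .67 | .10 | .35 |
| 10 | .48 | .60 | .03 | .22 |

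Gain in mean power per outcome over the wider range:
- **Every outcome responds:** +4.8 points (k = 2, correlation .8) to +12.3 points (k = 6, correlation 0).
- **Half respond, k = 4 to 10:** about +2 to +3.5 points. For k = 4 with two affected and correlation .3, .61 to .63.
- **One responds:** 0 to about +0.2 points.

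Correlation generally shrinks the gain. For k = 4 with all affected it is about +11 points at correlation 0, +10 at .3, +9.6 at .5 and +8.5 at .8.

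**Step 4. Family-wise error.** With no true effects the two rules agree (about .048 at k = 4, correlation .3; .05 within simulation noise when outcomes are independent). With some true effects at correlation .3, single-step versus Holm-Sidak:
- k = 2, one affected: .025 versus .041
- k = 4, two affected: .025 versus .038
- k = 6, three affected: about .024 versus .036

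Both rules stay below .05.

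**The case against.** The strongest reply is that nothing here is wrong. Single-step Sidak controls the error it claims to control and has simple matching simultaneous intervals, which is a legitimate reason to prefer it. That stands, and it makes this an efficiency option rather than a defect.

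Four stronger readings are tempting, and the documents do not support them.

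- A reader might infer that the plan forfeits a fixed amount of power, of the order of 5 to 12 points. That range needs every bar-level outcome to carry the full detectable effect. The plan makes no such assumption and gives neither k nor the correlation. With one responding outcome the gain is essentially nil.
- A reader might infer that the single-step rule buys nothing in error control. The nominal bound is the same, but step 4 shows lower actual error when only some outcomes respond.
- A reader might infer that correlation between outcomes strengthens the case. It generally reduces the gain.
- A reader might infer that the plan rules out a step-down form. It names only the Sidak procedure; single-step is the default reading, not an explicit choice.

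It is also fair to object that the change leaves a larger gap open: the bar-level power figures take no account of the planned correction, and the number of tests is not fixed. Under single-step Sidak the effect detectable with 80% power becomes d = 0.73 to 0.84 for k = 2 and 0.79 to 0.91 for k = 4. Holm-Sidak recovers only part of the loss; even at k = 2 with both outcomes affected, mean power per outcome is about 77%.

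**Conclusion.** The point holds as a cheap, optional improvement. That Holm-Sidak makes every single-step rejection under the same nominal bound requires no assumption about k or the effects. It does assume that the plan means single-step Sidak and that the dependence conditions behind Sidak's inequality hold, which both forms need equally. The size is conditional on the assumed α, k and correlations and on how many outcomes respond: 0 to about 12 points per outcome, and largest when all of them do. The plan's present choice is not an error.

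**What to change.** In the last sentence of Bar-level Analyses, replace the name of the procedure with the Holm-Sidak step-down procedure. Leave the rest of the sentence, including its study-wise scope, unchanged, so that the correction covers the same family of tests the plan already intends. Report step-down adjusted p-values. Make the change before bar-level outcomes are compared by arm. If single-step Sidak is preferred for its intervals, say so explicitly; that also removes the ambiguity.

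The cost is one edited phrase and no extra bars or data. The downside is that step-down testing has no simple matching simultaneous intervals. Per-outcome 95% intervals would have to be labelled descriptive and may disagree with the adjusted p-values. The edit does not restore 80% power at the stated effects, so the power statement needs separate attention.
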